14.3 Date Imputation

14.3.1 Prior and Concomitant Medication

Prior and concomitant medications will be coded using the WHO Drug Dictionary version Sep2017 or later. For the purpose of inclusion in prior and/or concomitant medication tables, incomplete medication start and end dates will be imputed as follows:

If the start date is incomplete, the following rules will be applied:

- If the day is missing (e.g. XXFEB2017), the month and year of the partial date will be compared to the date of illness onset.
 - If the month and the year are equal for both dates, the start date will be imputed as the earlier date of: (i) the date of illness onset, or (ii) the recorded end date of the medication. If the recorded end date is missing, the start date will be imputed as the date of illness onset.
 - If the month or year is not equal for both dates, the start date will be imputed as the first day of the month (e.g. 01FEB2017).
- If the day and month are missing (e.g. XXXXX2017), the year of the partial date will be compared to the date of illness onset.
 - If the years are equal for both dates, the start date will be imputed as the earlier date of: (i) the date of illness onset, or (ii) the recorded end date of the medication. If the recorded end date is missing, the start date will be imputed as the date of illness onset.
 - If the years are not equal for both dates, the start date will be imputed as the first day of January of the year (e.g. 01JAN2017).

If the end date is incomplete the following rules will be applied:

- If the day is missing (e.g. XXFEB2017), the month and year of the partial date will be compared to the date of End of Study (EOS).
 - If the month and the year are equal for both dates, the end date will be imputed as the later date of: (i) EOS, or (ii) the recorded/imputed start date of the medication.
 - If the month or year is not equal for both dates, the end date will be imputed as the last day of the month (e.g. 28FEB2017).
- If the day and month are missing (e.g. XXXXX2017), the year of the partial date will be compared to the date of End of Study (EOS).
 - If the years are equal for both dates, the end date will be imputed as the later date of: (i) EOS, or (ii) the recorded/imputed start date of the medication.
 - If the years are not equal for both dates, the end date will be imputed as the last day of the year (e.g. 31DEC2017).
- In the case of the death of a subject, if the imputed end date is after the date of death, the end date will be imputed as the date of death.

For the missing day imputation, the following examples should be used for reference:

- Example 1:
Medication start: UNJUN2017
Medication end: 20OCT2017
Date of illness onset: 16OCT2017
Medication start imputed: 01JUN2017
- Example 2:

Statistical Analysis Plan

Medication start: UNOCT2017
Medication end: 20OCT2017
Date of illness onset: 16OCT2017
Medication start imputed: 16OCT2017

- Example 3:

Medication start: UNOCT2017
Medication end: 20OCT2017
Date of illness onset: 24OCT2017
Medication start imputed: 20OCT2017

14.3.2 Symptom Relief Medication

The start date imputation will follow the same rules applied for the prior and concomitant start dates. The end date imputation will also follow the same rules applied for the prior and concomitant end dates, except that the partial dates will be compared to the dates of Day 8 instead of EOS. For subjects with suspicious ADE, the same rules will be applied, but last date of suspicious ADE assessment will be used instead of Day 8.

To determine the start time for resolution of symptom and fever in primary efficacy analysis, incomplete first and last taken time of symptom relief drug will be imputed as follows:

Route	Frequency	Time of first taken	Time of last taken
Oral Respiratory(Inhalation) Intramuscular Ophthalmic	Once, Daily	08:00	08:00
	BID	08:00	20:00
	TID	08:00	20:00
Intravenous	Once, Daily	08:00	23:59
	BID	08:00	23:59
	TID	08:00	23:59

※ If a symptom relief drug was administered once intravenously and single dose is 2g then missing last taken time will be imputed as the first taken time.

Statistical Analysis Plan

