5.9.3 Permitted Drugs

During the study, unless contraindicated, subjects may take acetaminophen/paracetamol, levodropropizine and chlorpheniramine for symptom relief according to the label's prescribing information and at dosages that do not exceed the manufacturer's recommendations. Those medication for symptom relief would be prescribed by investigators as P.R.N (pro re nata). The investigator should train the subject to administer maximum twice a day as much as possible. And administration of the medication during the study should be reported on the diary. Subject will be not allowed to use other drugs for symptom relief except acetaminophen/paracetamol, levodropropizine and chlorpheniramine.

If these drugs are taken, details concerning the dose and duration of treatment will be recorded in the subject's medical records (source documents) and in the eCRF.

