10.1 Primary Efficacy Analysis

The primary efficacy endpoint analysis will assess the time from the administration of study drug to resolution of influenza symptoms and fever. The Flu-iiQ™ and body temperature recorded in diary including records as

Statistical Analysis Plan

a part of suspicious ADE assessment will be used for the analysis. The Flu-iiQ™ is a validated questionnaire with four domains. This includes the Domain 1; intensity of influenza symptoms, Domain 2; impact on activities, Domain 3; effects on feelings and Domain 4; concerns due to influenza. Subjects are offered four choices, ranging from the most positive response (e.g., none or not at all) to the most negative choice (e.g., severe or great difficulty). This analysis will be performed on the ITTI population.

The definitions of resolution of influenza symptoms and fever are described below.

Resolution of symptoms has occurred if all of the following influenza symptoms (as recorded on the Flu-iiQ™ of Domain 1) are mild in intensity or none for at least 24 hours. (4-point scale - 0: None, 1: Mild, 2: Moderate, 3: Severe).

- Respiratory symptoms (cough, sore throat, and nasal congestion)
- Constitutional symptoms (headache, feeling feverish, body aches and pains, and fatigue)

Resolution of fever is defined as:

- Body temperature (as recorded in the diary) of $<37.0^{\circ}\text{C}$ for at least 24 hours.

The start time for resolution of influenza symptom and fever is defined as the start time when symptoms and fever are resolved, whichever occurred latest.

The time (in days) from the administration of study drug to resolution of influenza symptoms and fever will be calculated as follows: [Start date/time of resolution of influenza symptoms and fever] – [Start date/time of study drug administration]. If time of completion of diary for Flu-iiQ™ and body temperature is missing then the time will be assumed to be 10:00 AM and 10:00 PM for Morning and Evening, respectively.

If the subject has received the drugs for symptom relief, the effective duration of the drugs for symptom relief should be considered in determining the start time for resolution of symptom and fever.

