For example, the study drug was administered at 12:00 on 1st day. The first time body temperature recorded $<37.0^{\circ}\text{C}$ in the diary was 10:00 on 2nd day and continued more than 24 hours. But acetaminophen/paracetamol known to be effective for 6 hours had been administered at 09:00 on 2nd day [1 hour prior to the time when the body temperature decreased $<37.0^{\circ}\text{C}$], it will be calculated that the start time point for body temperature $<37.0^{\circ}\text{C}$ is 15:00 on 2nd day [27 hours after the study drug administration]. Then, if the next time body temperature recorded $<37.0^{\circ}\text{C}$ in the diary since 15:00 was 22:00 on 2nd day and body temperature was $<37.0^{\circ}\text{C}$ for 24 hours from then, the start time for resolution of fever is 22:00 on 2nd day [34 hours after the study drug administration].

Drugs for symptom relief will be discussed during blinded DRM (14.5). Only drugs for symptom relief with an effective duration overlapping the primary endpoint duration (from a day of resolution start to resolution end) will be considered as drugs that affect the result of primary efficacy analysis. Effective durations of each drug will be discussed during blinded DRM too.

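### A symptom-relief drug with an unknown end day is imputed as taken until Day 8 or later if its recorded month is that of Day 8, which can censor a recovered subject in the primary analysis

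*SAP*

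**What the plan says.** SAP 14.3.1 gives date rules meant for sorting drugs into prior and concomitant medication tables. If the end day is missing and the month and year match the end of study, "the end date will be imputed as the later date of: (i) EOS, or (ii) the recorded/imputed start date of the medication". Otherwise, "If the month or year is not equal for both dates, the end date will be imputed as the last day of the month".

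SAP 14.3.2 applies these rules to symptom-relief drugs, "except that the partial dates will be compared to the dates of Day 8 instead of EOS". For subjects under suspicious-ADE assessment, "last date of suspicious ADE assessment will be used instead of Day 8". For the primary analysis, "incomplete first and last taken time of symptom relief drug will be imputed as follows": the last time is 08:00 (once or daily) or 20:00 (twice or three times daily) for non-intravenous routes, and 23:59 for intravenous ones. Once and daily share a row.

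SAP 10.1 makes these dates matter: "the effective duration of the drugs for symptom relief should be considered in determining the start time for resolution of symptom and fever". A drug counts if it is one "with an effective duration overlapping the primary endpoint duration (from a day of resolution start to resolution end"). SAP 14.5 lists effective durations from 0 to 32 hours; paracetamol has 6 or 8. Subjects without resolution are censored at the last diary entry, and any censoring replaces the Wilcoxon rank-sum test with the log-rank and Gehan tests.

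Protocol 5.9.3 makes relief drugs as-needed, "Those medication for symptom relief would be prescribed by investigators as P.R.N (pro re nata"), and requires their use to be reported in the diary, which runs from Day 1 to Day 8.

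**The concern.** In a medication table a late end date does no harm, because the drug is concomitant either way. In the primary endpoint it decides whether a subject can have the event. A gap in one medication record can turn a single as-needed dose into a week of use, and so turn a recovered subject into a censored one.

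The overlap condition in SAP 10.1 does not screen this out, because a drug imputed to Day 8 overlaps any resolution that begins after the drug started. No planned analysis would reveal the effect. The added sensitivity analyses in SAP 10.1 change only the fever condition, the two approaches in SAP 10.3.1 concern missing Flu-iiQ items, and SAP section 13 does not mention this rule. At stake is lost power in a comparison planned at 80%.

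**Working it through.** **The plan's own example (SAP 10.1).** Infusion is at 12:00 on Day 1, and one paracetamol dose with a 6-hour effect is taken at 09:00 on Day 2. The effect ends at 09:00 + 6 h = 15:00 on Day 2, which is 27 h. The next entry, at 22:00 on Day 2, is 34 h. Both figures match the SAP.

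**The same record with the end day missing.** Take Day 1 as 1 February and Day 8 as 8 February, with oral frequency Once and the end recorded only as February.
- Month and year match Day 8, so the end date is the later of Day 8 and the start, which is Day 8.
- With the clock time also missing, the last dose is put at 08:00 on Day 8, and the effect ends at 08:00 + 6 h = 14:00 on Day 8.
- With entries at 10:00 and 22:00, the last entry is 22:00 on Day 8, so a 24-hour run must begin by 22:00 on Day 7. That is inside the mask if masking is continuous.
- Before the dose there is only the 22:00 entry on Day 1, so no earlier run exists.
- Result: an event at 34 h becomes censoring at 7 × 24 + 10 = 178 h.

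**How general this is.** The rule was coded on that diary with continuous masking, for drug start days 1 to 8, once-daily or twice-daily dosing, and effects of 6, 12 and 32 h. On the same-month branch, no 24-hour unmasked run remained after the drug started in any case. For suspicious-ADE subjects the reference date moves with the extended diary, so the extra entries need not restore a usable run.

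**Where it does not apply.**
- *Earlier month recorded.* Day 1 is 28 January, Day 8 is 4 February, and twice-daily paracetamol truly ends on Day 2 but is recorded as January. The end becomes 31 January (Day 4) at 20:00, masking lasts to 02:00 on Day 5, and the next entry, at 10:00 on Day 5, is 94 h. The event is delayed (46 h with the true end) but still possible. If dosing days are equally likely over October to April of two seasons (an assumption), the imputed end falls before Day 8 for 23.1% of dosing dates when the true end is Day 1, declining to 0% when it is Day 8.
- *Run before the first dose.* With a drug start on Day 3 or later, a subject resolved from 22:00 on Day 1 keeps the event at 10 h. With a start on Day 1 or Day 2 none is possible.
- *Products with 0 h duration.* The SAP does not say whether these mask anything.
- *Per-dose masking.* With doses at 08:00 and 20:00 and a 6-hour effect, entries at 07:00 and 19:00 are all usable, while entries at 10:00 and 22:00 are all masked. The result then depends on when the subject fills in the diary.

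**Size, as an illustration.** The design figure first: δ/SE = 1.8 / [3 × √(1/63 + 1/38)] = 2.92, so power is Φ(2.92 − 1.96) = 83.2%. Allowing for Wilcoxon efficiency 3/π, it is Φ(2.92 × √(3/π) − 1.96) = 81.4%, close to the stated 80%.

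The simulation compares 63 with 38 subjects by log-rank test, using gamma times with means 3.2 and 5.0 days and SD 2.7. The diary ends at 7.5 days and affected subjects are censored there. Only the group sizes and the 1.8-day difference come from the SAP. The means, the SD (the SAP has 3) and the affected shares are assumptions.

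| Share losing the event, both arms | Subjects of 101 | Power |
|---|---|---|
| 0% | 0 | about 85% |
| 1% | 1 | about 83% |
| 2% | 2 | about 80% |
| 5% | 5 | about 73% |
| 10% | 10 | about 60% |

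Repeat runs fall within about 3 points of these values. With SD 3 the starting power is about 79%. The share is of subjects who actually lose the event, which cannot exceed the share with a partial end date.

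**The case against.** The strongest reply is that partial end dates should be rare. The window is eight days. Relief use goes into a diary that site staff review, discrepancies are queried, all entries are source-verified (Protocol 6.1.1, 7.1, 11.1.2), and relief drugs are discussed at the blinded data review meeting. At a 1% share the illustrated loss is 2 points. This stands as a limit on the likely size, since no document reports such a record.

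A second reply is that assuming later use is cautious, because it prevents drug-suppressed fever or symptoms from counting as resolution. That has force for a drug taken over several days with no diary record, and it is why the Day 8 rule can stay there. It has none for a drug recorded as taken once. SAP 14.3.2 already sets last time equal to first time for one such case, a single 2 g intravenous dose, but for clock time only.

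A third reply is that the missing as-needed row concerns times, not dates, and that the protocol's advice of at most twice-daily use fits the twice-daily row. That is correct, and the point does not rest on it.

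Two stronger readings are tempting. A reader might infer that any partial end date makes the primary event impossible. The different-month branch, runs before the first dose and the unstated masking rule all contradict that. A reader might also infer a raised false-positive rate, on the ground that sicker placebo subjects take more relief drugs. With no drug effect, nothing in a blinded randomised trial makes the affected shares unequal, and with equal shares of 2% and 5% simulated type I error stayed nominal (4.2% to 6.0%).

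**Conclusion.** The point holds in limited form. On the same-month branch the rule gives a wrong end date for a drug taken once and an unsupported one for other as-needed use. Under continuous masking it then removes any event after the drug starts. Imputing first and last taken times implies continuous masking, but the SAP's only worked example masks a single dose, so the missing statement is itself a gap.

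The effect on the trial cannot be computed, because the number of partial records is not given. The power figures show only what equal shares would cost under the assumed distributions: about 2 points at 1% and about 12 at 5%. One such record would also switch the primary test if no other subject were censored. The change is worth making because the rule feeds the primary endpoint, no planned analysis tests it, and the correction is cheap.

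**What to change.** In SAP 14.3.2, for symptom-relief drugs with an unknown end day:

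1. If the frequency is Once, set the end date equal to the start date. This needs a recorded start day: if that is missing too, SAP 14.3.1 can put the start at illness onset, and the record should go to rule 2 or 3.
2. Otherwise, if the diary records doses, set the end to the last diary day with a recorded dose.
3. If there is no diary entry, keep the Day 8 rule as primary and add a sensitivity analysis that masks one effective duration from the start.
4. State whether masking is continuous from first to last dose or applies after each dose, and whether 0 h products mask anything.

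The cost is SAP wording and one extra run. Under rule 2 a few later doses that the subject did not enter in the diary may go unmasked. The one-duration mask in rule 3 is less cautious than the Day 8 rule, which is why it is proposed only as a sensitivity analysis.

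### SAP 14.3.2: for non-intravenous Once/Daily relief drugs, a missing last-taken time becomes 08:00 with no check against a later recorded first-taken time

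*SAP*

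**What the plan says.** SAP 10.1 requires that "the effective duration of the drugs for symptom relief should be considered in determining the start time for resolution of symptom and fever". A reading inside a drug's effective window does not start resolution; the next qualifying reading after the window does.

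SAP 14.3.2 supplies the clock times this needs when they are not recorded: "incomplete first and last taken time of symptom relief drug will be imputed as follows". For oral, inhaled, intramuscular and ophthalmic drugs the first row is "Once, Daily 08:00 08:00" (first time, then last time). The BID and TID rows for those routes use 08:00 and 20:00. The intravenous rows use 08:00 and 23:59.

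One note ties the last time to the first. It covers a drug "administered once intravenously and single dose is 2g then missing last taken time will be imputed as the first taken time". No other route or dose has such a rule.

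The date rules do check order. Under SAP 14.3.1, when month and year match, an incomplete end date becomes the later of the end-of-study date and the recorded or imputed start date. SAP 14.3.2 carries this over with Day 8 in place of end of study. The table of clock times has no equivalent.

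Protocol 5.9.3 describes how these drugs are used: "Those medication for symptom relief would be prescribed by investigators as P.R.N (pro re nata"), with subjects trained to take them at most twice a day as far as possible.

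**The concern.** A single as-needed dose is naturally recorded with one clock time. If that time is entered as first taken and the last-taken field is blank, the Once/Daily row puts the last dose at 08:00. For an afternoon or evening dose, the record then says that the last dose came before the first.

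The window is counted from the last-taken time, so it is displaced by the gap between 08:00 and the actual dose. A temperature or symptom score recorded while the drug was working can then count as unmasked and become the start of resolution, which is what the SAP 10.1 rule is meant to prevent. A multi-day Daily record of an evening drug has a related problem: its last dose is placed at 08:00 on the end date, ahead of the usual evening dose.

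The error enters the derivation of the primary event time. The planned sensitivity analyses that drop fever or change its threshold are assessed in the same way as the primary endpoint, so they appear to inherit it.

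**Working it through.** **Inputs**
- Worked example: infusion at 12:00 on Day 1, 6-hour drug at 09:00 on Day 2, readings at 10:00 and 22:00 (SAP 10.1).
- Imputed times: non-intravenous Once/Daily 08:00 and 08:00; BID and TID 08:00 and 20:00 (SAP 14.3.2).
- Effective durations: paracetamol 6 h or 8 h by single dose; non-zero entries run from 6 h to 32 h (SAP 14.5).
- Diary times: about 06:00–10:00 and 18:00–22:00 (SAP 14.1, footnotes 18 and 19).
- Planned effect: 1.8 days (SAP 5.2), used only for scale.

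**Formulas**
- Window end = last-taken time + effective duration.
- Start of resolution = first qualifying diary reading at or after the window end.

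**1. The SAP's own example.** The text has "acetaminophen/paracetamol known to be effective for 6 hours had been administered at 09:00 on 2nd day". 09:00 + 6 h = 15:00 on Day 2, which is 12 + 15 = 27 h after infusion. The next reading, at 22:00, is 12 + 22 = 34 h. The SAP states the same: "the start time for resolution of fever is 22:00 on 2nd day [34 hours after the study drug administration".

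**2. The same example, recorded as Once with the last time blank.** 08:00 + 6 h = 14:00, or 26 h instead of 27 h. The 10:00 reading is still masked and the start stays at 34 h. A dose after 08:00 does not by itself change the result.

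**3. Later doses.** 6-hour drug; readings at 20:00 and at 08:00 next day, both assumed to qualify.

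| Recorded first dose | Window end, table | Window end, last = first | Start, table | Start, last = first | Difference |
|---|---|---|---|---|---|
| 09:00 | 14:00 | 15:00 | 20:00 | 20:00 | 0 h |
| 13:00 | 14:00 | 19:00 | 20:00 | 20:00 | 0 h |
| 15:00 | 14:00 | 21:00 | 20:00 | 08:00 next day | 12 h |
| 17:00 | 14:00 | 23:00 | 20:00 | 08:00 next day | 12 h |
| 19:00 | 14:00 | 01:00 next day | 20:00 | 08:00 next day | 12 h |

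**4. Which dose times can release a masked reading.** A reading is wrongly released if it falls at or after the table's window end, not before the dose, and before dose + duration. On a half-hour grid:
- 6 h drug (table window ends 14:00): doses from 12:30 (12:30 + 6 h = 18:30, past an 18:00 reading) to 22:00, the last evening reading. Later doses wear off before 06:00 (23:30 + 6 h = 05:30).
- 8 h drug (table window ends 16:00): doses from 10:30 (10:30 + 8 h = 18:30) to 23:30, the last point on the grid. For doses after 22:00 the released reading is the next morning's (22:30 + 8 h = 06:30).

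**5. When the window ends before the dose.** This needs a dose later than 08:00 + duration: after 14:00 (6 h), 16:00 (8 h) or 20:00 (12 h). Otherwise the window is only too short. For 24 h and 32 h drugs it ends the next day, so it cannot precede a same-day dose.

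**6. BID and TID rows.** For a 6 h drug the window ends at 20:00 + 6 h = 02:00 and no diary reading is affected. For longer durations only a first dose recorded after 20:00 can be misordered.

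**7. Scale.** The documents do not give the share of subjects affected. Assume 1% to 20% of an arm, each shifted by 12 h = 0.5 day. The arm mean moves by 0.01 × 0.5 = 0.005 day to 0.20 × 0.5 = 0.10 day, or 0.005/1.8 = 0.3% to 0.10/1.8 = 5.6% of the planned effect.

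**The case against.** The strongest objection is that this is an edge case. It needs a non-intravenous Once/Daily record, a recorded first time, a blank last time, a late enough dose, a diary reading in the gap, and both components of the endpoint resolved. Protocol 6.1.1 has staff review the diary for omissions, and Protocol 11.1.2 has all entries checked against source. If both times are missing, 08:00 and 08:00 are at least consistent with each other. The SAP also does not say outright that the table applies when only the last time is missing.

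Most of this stands and limits the size of the point. It does not close the gap. The sentence introducing the table allows the last-time-only reading, and the intravenous note supports it by dealing with a missing last time on its own. Diary review and source checking do not guarantee complete times. The blinded review described in SAP 10.1 covers the drugs and their effective durations, not the order of taken times.

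A reader might go further in several ways that the documents do not support:
- **That 08:00 applies to every non-intravenous record.** BID and TID use 20:00, and training to take at most two doses a day makes BID records plausible.
- **That every dose after 08:00 brings resolution forward.** Steps 2 and 3 show no change for morning and early-afternoon doses of a 6 h drug with a 20:00 reading.
- **That 24-hour drugs suffer more.** The displacement is the recorded first time minus 08:00, whatever the duration.
- **That as-needed records have no rule.** The prescription is as needed, but the documents do not show how the eCRF codes frequency.
- **That the rule dilutes the treatment effect.** No text says placebo subjects take more relief drug. The rule is the same in every arm, and the intravenous 23:59 entry acts in the opposite direction.

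**Conclusion.** The point holds for one row of the table. For oral, inhaled, intramuscular and ophthalmic drugs recorded as Once or Daily, SAP 14.3.2 can place the last dose before a recorded first dose on the same day, and nothing in either document prevents it. For 6 h and 8 h drugs taken from about midday onward, a reading that should be masked can then start fever or symptom resolution.

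The primary time moves, by about 12 h in the cases worked above, only when symptoms and fever both then meet the 24-hour criterion, because SAP 10.1 takes the later of the two starts. If the other component resolves later anyway, the shift is smaller or zero.

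The overall effect cannot be computed from the documents. The range of 0.005 to 0.10 day rests on an assumed 1% to 20% of subjects, and the true figure is probably small. The direction of any difference between arms is unknown. The rule still deserves correction because it can produce an impossible record in the primary endpoint derivation and is simple to repair.

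**What to change.** Add to SAP 14.3.2, before unblinding:
- An imputed last-taken time may never be earlier than a recorded first-taken time on the same date.
- For a Once dose by the oral, inhaled, intramuscular or ophthalmic route, a missing last-taken time equals the recorded first-taken time.
- For a Daily drug by these routes, a missing last-taken time is the recorded first clock time on the end date.
- The 08:00 default for the last-taken time is used only when both times are missing.

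The cost is a few sentences and a small programming change, with no new data. Protocol 8.3 already requires the SAP to be final before database lock and unblinding. A blinded listing of non-intravenous Once/Daily records with a recorded first time and a blank last time would show at the data review meeting how many are affected.
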